We hypothesize that, in older adults, intervening on SB will be more effective for preventing weight regain than the conventional approach of intervening on exercise behavior. This is supported by evidence showing: 1) decreased SPA/increased SB is a consistent biological adaptation to weight loss³¹⁻³⁹ and this adaptation predicts weight regain;⁴⁰ 2) as our data show, reducing SB with a self-monitoring intervention enhances weight loss and may prevent weight regain⁴¹; 3) interventions targeting increased exercise are less tolerated and sustained over time in older, obese adults⁴²⁻⁵⁰ who may be more likely to adhere to a SB intervention; 4) initiation of exercise in older adults can lead to compensatory increases in SB,⁵¹⁻⁶⁶ thus reducing total energy expenditure and limiting its efficacy for preventing weight regain; and 5) compensatory eating occurs in many individuals who exercise,^{56,67,68} though the effects of altering SB on appetite and energy intake are not known.

Objectives

Our pilot data provide evidence that a novel, highly acceptable, behavioral intervention (SitLess) that focuses on increased awareness of SB employing accelerometry-based self-monitoring, that is reinforced with other self-regulatory strategies, improves weight loss during treatment and prevents weight regain during a short (5-month) follow-up.⁴¹ **The main goal of this study is to definitively test the efficacy of this intervention for longer-term maintenance of lost weight.** This will be an 18-month trial in up to 189 obese (BMI=30-45 kg/m²) older (65-85 years) adults randomized to one of three treatment arms, all with a caloric restriction intervention for weight loss (WL) plus: 1) moderate-intensity aerobic exercise (WL+EX); 2) a SB intervention (WL+SitLess); or

3) (WL+EX+SitLess). Participants will undergo a 9-month weight loss intervention involving a 6-month intensive phase with decreasing contact from months 7 to 9, and a minimal contact, self-managed, 9-month follow-up phase to address these **aims and hypotheses**:

Aim 1: To determine whether addition of an intervention that targets sedentary behavior to a standard WL intervention that only targets EX results in a larger 18-month reduction in body weight in older, obese adults.

Primary hypothesis: WL+EX+SitLess will have lower 18-mo body weight than either WL+EX or WL+SitLess.

Secondary hypothesis: WL+SitLess will have lower 18-mo body weight than WL+EX.

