12. Ecological Momentary Assessment: Increasingly researchers are recognizing the large degree of variability within the individual, and within the day, and the role this variability has on intervention efficacy. Therefore, ecological momentary assessment (EMA) will be used to study within-person and within-day interactions between sleep quality and duration (assessed via items from the Pittsburgh sleep quality inventory), feeling states (i.e., calmness, fatigue, relaxation, tiredness, assessed via items from the exercise-induced feelings inventory), affect (assessed via the feelings scale), level of hunger (assessed by asking current level of hunger), and craving for food (assessed by asking current craving for favorite meals or snack foods).

Prior to the start of the intervention and following the initial 9-month intervention period, participants will complete week-long daily assessments. These data will align with ActivPAL monitoring. Because data collected via the study EMA website are time-stamped, they will be time-matched to the hourly ActivPAL data. Participants will be instructed to complete assessments upon waking up in the morning and immediately prior to going to bed at night.

Additionally, each participant will receive up to five daily text message prompts with links to secure web-based questionnaires. Each assessment will take the average user less than two minutes to complete, and will contain all items with the exception of sleep items, which will be assessed only during the first assessment of the day.

13. A Technology survey and Intervention survey will be administered at 9 months and 18 months assessment visits to gain insight on the participants opinion of the technology and group dynamic used in this study.

Statistical Analyses

Sample size: The sample size chosen for this study (n=180; 60/group) provides >85% statistical power (with estimated 51 completers per group, see Table) to definitively test our Primary Hypothesis. In our pilot project, the adjusted mean group weight difference after 10 months (5 months of weight loss and 5 months of follow-up) was 3.6 kg (95% CI= 1.2-6.0 kg). Thus, with the longer 18-month time frame in the proposed study, we anticipate there could be a mean group

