Table 5. Power to detect significant differences in mean change ($\alpha=0.05$ level; 2-sided test, Bonferroni adjustment for multiple comparisons) between groups using ANCOVA, adjusting for sex; Baseline SD and pre-post correlations (adjusted for sex) were calculated using data from obese, older persons enrolled in our pilot.

Outcome	Group Comparison	Pre-Post Correlation	SD	Mean 18-mo grp difference	Effect Size (diff/SD)	Power	
							51/grp (85% retention)
Weight (kg)	WL+EX+SitLess vs. WL+EX & WL+SitLess ($\alpha=0.025$)	0.87	8.2	2.7	0.33		0.87
	4			0.49		>0.99	
	WL+SitLess vs. WL+EX ($\alpha=0.05$)	0.87	8.2	2.3	0.28		0.81
				2.5	0.30		0.87

difference between WL+EX+SitLess and WL+EX or WL+SitLess of ~4 kg; however, we will have power to detect a mean group difference as little as 2.7 kg. This corresponds to 3.0-4.4% of the baseline weight for a 90 kg person and is considered clinically meaningful. We also anticipate that the WL+SitLess group will regain less weight than WL+EX, and will have >85% power to detect a mean group difference as small as 2.3 kg (not adjusted for multiple comparisons). Based on our prior 18-month exercise and diet trials in similar populations,^{8,70} we expect no more than 15% drop-out. In addition, with 51/grp, we have at least 80% power to detect effect sizes of 0.49-0.52 for our Aim 2 outcomes (physical activity energy expenditure, and minutes of SB and SPA), under ANCOVA with repeated measures (to estimate the time-averaged difference in response), assuming a compound symmetry covariance structure, and effect sizes of 0.24-0.49 for our Aim 3 outcomes under ANCOVA models as for the primary aim.

Database management: All data except those generated from the activity monitors will be entered into the web-based study database as collected. Our data entry system will protect confidentiality and data security and the use of text containing identifying information will be avoided. Activity monitor data will be downloaded to a server and the summary data merged with other study data. Final analysis datasets will be stored in SAS. All data will undergo range checks at the time of data entry and will be examined periodically by histograms and bivariate scatterplots to check for inconsistencies, unusual data needing further verification, and outliers. Plots of longitudinal observations will be used to inspect for unusual changes that need to be verified against source documents.

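### The text claims over 85% power at 2.3 kg for WL+SitLess vs WL+EX; Table 5 gives 0.81, and recomputation agrees with the table

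*Combined protocol and SAP*

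**What the plan says.** The secondary hypothesis under Aim 1 (Objectives) is that "WL+SitLess will have lower 18-mo body weight than WL+EX". Its power is stated twice under Statistical Analyses, Sample size.

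- **Text:** the trial "will have >85% power to detect a mean group difference as small as 2.3 kg (not adjusted for multiple comparisons".
- **Table 5:** the rows for "WL+SitLess vs. WL+EX" at alpha 0.05 use a correlation of 0.87 and an SD of 8.2 kg. They give power of 0.81 at 2.3 kg and 0.87 at 2.5 kg. The labelled power column is for 51 per group at 85% retention, and the caption specifies a "2-sided test, Bonferroni adjustment for multiple comparisons". For this comparison alpha is left at 0.05, which agrees with the text's remark that no adjustment is made.

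The basis for the number of completers is given in the same section: 180 randomized, 60 per group, "with estimated 51 completers per group, see Table", and "we expect no more than 15% drop-out".

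**The concern.** The sentence and the table describe one calculation (same arms, same difference, same alpha) and give different answers. Only one can be right on the stated basis.

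A reader who relies on the sentence would put the risk of missing a true 2.3 kg difference below 15%. By the table it is 1 - 0.81 = 19%. This matters mainly when a null result is interpreted for the head-to-head comparison of SitLess with conventional exercise, or when the sentence is copied into a report without the table.

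**Working it through.** **Inputs.** From Table 5: SD 8.2 kg, pre-post correlation 0.87, two-sided test, alpha 0.05 for this comparison and 0.025 for the primary one. From the Sample size text: 60 per group and 15% drop-out, so 60 × 0.85 = 51 completers per group.

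**Formulae.** For ANCOVA with baseline weight as covariate:

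- Residual SD = SD × √(1 - r²) = 8.2 × √(1 - 0.87²) = 4.043 kg
- SE of a two-group difference = 4.043 × √(2/51) = 0.801 kg
- Normal-approximation power = Φ(difference/SE - z), with z = 1.960 at alpha 0.05 and 2.241 at alpha 0.025
- The same was run with the noncentral t, using residual degrees of freedom for two arms (98) and for three arms (148)

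**Reproducing Table 5 at 51 per group.**

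| Difference | Alpha | Normal | Noncentral t | Table 5 |
|---|---|---|---|---|
| 2.7 kg | 0.025 | 0.871 | 0.862 to 0.865 | 0.87 |
| 4 kg | 0.025 | 0.997 | 0.996 to 0.997 | >0.99 |
| 2.3 kg | 0.05 | 0.819 | 0.812 to 0.814 | 0.81 |
| 2.5 kg | 0.05 | 0.878 | 0.871 to 0.873 | 0.87 |

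All four rows reproduce to within 0.01. For the disputed row by hand: 2.3/0.801 = 2.87, 2.87 - 1.96 = 0.91, and Φ(0.91) ≈ 0.82.

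**What 85% would need.**

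- Difference at 51 per group: 0.801 × (1.960 + 1.036) = 2.40 kg by normal approximation, 2.42 kg by t.
- Completers at 2.3 kg: 2 × (4.043/2.3)² × (1.960 + 1.036)² ≈ 55.5, so 56 per group by normal approximation. With 15% drop-out that is 56/0.85 = 65.9, so 66 randomized per group, or 198 in all. This exceeds both the planned 180 and the maximum of 189.

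**Could another reading of the inputs rescue the sentence?**

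- *Maximum enrolment.* The Objectives allow up to 189. 189/3 × 0.85 = 53.6 completers per group. Power at 2.3 kg is 0.827 by t (0.834 normal) with 53, and 0.834 (0.840) with 54.
- *Rounding of SD and correlation.* SD 8.15 to 8.25 and correlation 0.865 to 0.875 give 0.794 to 0.830 by t (0.801 to 0.837 normal).
- *Rounding of the difference as well.* 2.349 kg with SD 8.15 and correlation 0.875, all at their most favourable, gives 0.846 by t (0.852 normal). That corner does not agree with the table's own 0.81.
- *Change-score analysis.* SD of change = 8.2 × √(2 × (1 - 0.87)) = 4.181 kg; power at 2.3 kg is 0.793.
- *One-sided test at 0.05.* Power is about 0.89, but the caption specifies two-sided.

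**The case against.** The strongest defence is that the sentence gives no number per group and may have been computed for all 60 randomized per group. At 60 per group, power at 2.3 kg is 0.871 by t (0.876 normal), which does exceed 85%. The Data analyses section says everyone randomized is analysed, so 60 is not an arbitrary choice. Table 5 also came through PDF reading with blank cells, so a second power column for full enrolment cannot be strictly excluded.

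This may explain how the figure arose, but it is not the basis the plan states. The paragraph opens by tying its power to 51 completers and the table, and the drop-out allowance follows straight after the disputed sentence. The only labelled power column is for 51 per group, and its values are 51-per-group values: at 60 per group the 2.3 kg and 2.5 kg rows would read about 0.87 and 0.92, not 0.81 and 0.87. The neighbouring claim about 2.7 kg also matches the 51-per-group figure. A simple mix-up of the 2.3 kg and 2.5 kg rows would explain the sentence equally well.

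Two parts of the defence stand. The sentence should state its number per group. And the practical consequence is small: a gap of about four percentage points, or 0.1 kg, with power still above 80%.

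**Conclusion.** The concern holds. On the plan's stated basis (51 completers per group, two-sided alpha 0.05, SD 8.2 kg, correlation 0.87), power at 2.3 kg is 0.81 by t or 0.82 by normal approximation. It is not above 0.85. Table 5 is correct and the sentence overstates the power.

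The conclusion assumes the ANCOVA variance formula, which the table's own figures support. Severity is minor: the primary-hypothesis power (0.87 at 2.7 kg), the sample size, alpha and the analysis are all unaffected.

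**What to change.** Restate the sentence with Table 5's own figures and its number per group, for example: *with 51 completers per group and no multiplicity adjustment, the comparison of WL+SitLess with WL+EX has 81% power at a true difference of 2.3 kg and 87% at 2.5 kg.*

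The cost is one reworded sentence and a slightly less favourable quoted power for the secondary hypothesis.

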Participants in all three groups will receive a Fitbit activity monitor, prior to the start of intervention, to assist with self-monitoring of their prescribed activity (e.g., aerobic exercise and/or decreased daily SB). As stated above, they will be encouraged to wear the Fitbit daily during the 9-month WL phase, and to wear it at least twice/week during the 9-month follow-up phase. If the monitor is lost, stolen or damaged they will be provided with a replacement. If a participant withdraws from the study, they will be asked to return the Fitbit. After completion of the last study visit, participants will be allowed to keep the Fitbit.

In addition, the study interventions require the use of a smartphone to upload data from the Fitbit and to access the study website to receive encouragement and motivation. If a participant does not own a smartphone or their smartphone is not compatible with our applications, the study will provide them with a smartphone and a phone/data plan for the length of their participation in the

study. Participants will be expected to keep the phone with them daily and to take care not to lose or damage it. Participants will be instructed that the phone is for study use only. If the phone is lost, stolen or damaged they will be provided with a replacement. If a participant withdraws from the study, they will be asked to return the smartphone and it will be deactivated immediately. After completion of the last study visit (V8), participants will return the smartphones and they will be deactivated.

Schedule of assessment visits

Assessments at baseline, after the intensive WL phase (6-months), after the entire 9-month WL intervention (9-months) and at study end (18-months) include: the primary outcome of body weight, as well as physical activity energy expenditure, light, moderate and vigorous activity minutes, and sedentary behavior minutes and breaks. The other secondary outcome assessments (RMR, physical function and measures of cardiometabolic risk) will be performed at baseline, after the intensive WL phase (6-months), and at study end (18-months) (See Table). At follow up, Visit 7 and 8 may be combined to help with participant burden and some questionnaires will be administered over the phone to limit the time in the clinic.

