The nature, purpose, and risks of all tests will be explained to participants prior to obtaining their written consent and prior to each test. All examiners will be blinded to participant treatment assignment and are trained in the standardized conduct of all tests. Standardized written instructions will be provided.

Study Measure(s)

1. Baseline demographic data will be recorded based on participant self-report. Medical information on prior and existing co-morbidities and hospitalizations will be ascertained by self-report and confirmed by direct query of the participant at the screening visit. We will also record medication use by asking participants to bring in all medications (including nutritional supplements).
2. Adverse events will be assessed by asking participants at each assessment visit, and during monthly phone or email contact with participants during the 9-month follow-up phase, to report any health changes, injuries, etc. and these will be recorded using the Adverse Event Form.
3. Body weight and composition: Body weight (the study's Primary Outcome) will be measured in our clinic on the same scale. Body composition, bone density, visceral fat will be measured by dual-energy X-ray absorptiometry (DXA; Hologic Discovery W, Bedford, MA). All scans will be performed and analyzed by our trained DXA technician who is certified by the International Society for Clinical Densitometry. Bone mineral density (BMD) will be measured using specific scans of the anterior-posterior spine (L1-L4) and proximal femur. Visceral fat area will be measured from the whole-body scan in a 5-cm wide region across the entire abdomen just above the iliac crest at a level approximate with the 4th lumbar vertebrae.⁷⁷
4. Resting metabolic rate will be assessed to determine participant's weight-maintaining energy needs for prescribing the 400 kcal/d energy deficit for WL and will be measured again at 6- and 18-months to determine its response to the interventions. RMR will be measured in the morning after an overnight fast (8 hour minimum of no food, beverage, alcohol, caffeine or strenuous exercise) by indirect calorimetry.⁴¹ Upon arrival, subjects are asked to lie quietly for 20-30 min before testing. Measurement of oxygen consumption and carbon dioxide production are collected continuously for at least 30 min and RMR is calculated using the Weir equation.⁷⁸

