Data analyses: Initial analyses will follow the “intent-to-treat” principle in which data from all randomized participants are analyzed according to their randomized groups. We will document withdrawal and compliance in detail. We will attempt to identify baseline covariates that predict

attrition and compliance, and if such covariates can be identified, the analyses may need to incorporate stratification by these factors to decrease bias. Aim 1 hypothesis will be tested using analysis of covariance (ANCOVA) to compare group differences in 18-mo body weight, adjusted for baseline weight, gender (used to stratify randomization), and treatment arm. Differences in least-squares means and associated 95% confidence intervals will be calculated. Bonferroni adjustment will be used to account for multiple comparisons.

Secondary analyses (Aims 2 & 3)—Hypotheses of Aim 2 secondary outcomes will be tested using ANCOVA with repeated measures, where within subject correlations will be accounted for by using a compound symmetry covariance structure. Differences in least-squares means and associated 95% confidence intervals will be calculated. Group differences in breaks in SB will be tested using a generalized linear model with repeated measures, since a Poisson distribution is a better fit for such count data. Linear regression will be used to examine whether total physical activity energy expenditure and sedentary behavior at 6-months is predictive of less weight regain at 18-months, adjusted for baseline body weight and gender.

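### The Aim 1 ANCOVA on 18-month weight has no stated method for missing 18-month weights and does not use the 6- and 9-month clinic weights

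*Combined protocol and SAP*

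**What the plan says.** Under Statistical Analyses, Data analyses, Aim 1 is tested by "analysis of covariance (ANCOVA) to compare group differences in 18-mo body weight, adjusted for baseline weight, gender (used to stratify randomization), and treatment arm", with a Bonferroni adjustment. The same paragraph adopts intention to treat: "data from all randomized participants are analyzed according to their randomized groups".

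It also has a provision on attrition. The plan states "We will document withdrawal and compliance in detail". If baseline covariates are found to predict attrition or compliance, "the analyses may need to incorporate stratification by these factors to decrease bias". No section gives an imputation, weighting or likelihood method, or a sensitivity analysis, for a missing 18-month weight.

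Weight is measured more often than this test uses. The Schedule of assessment visits reads "Assessments at baseline, after the intensive WL phase (6-months), after the entire 9-month WL intervention (9-months" and then "at study end (18-months) include: the primary outcome of body weight". Study Measure(s), item 3, says body weight "will be measured in our clinic on the same scale". The Weight Loss intervention section adds that weight is recorded at every group session (weekly in months 1-6, bimonthly in months 7-9). From month 10 to month 18 the only contact is a monthly call or email.

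A repeated-measures approach is already planned elsewhere: "Hypotheses of Aim 2 secondary outcomes will be tested using ANCOVA with repeated measures".

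**The concern.** A model with one outcome per person cannot include a person who lacks that outcome. The intention-to-treat sentence says everyone randomized is analyzed, and the Aim 1 model does not say how.

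The available-case contrast remains unbiased in three situations:
- dropout is random;
- dropout depends only on the model's own covariates (baseline weight, sex, arm), given that the linear model holds;
- dropout depends on post-baseline weight in the same way and at the same rate in all arms.

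It can be biased when dropout depends on post-baseline weight beyond those covariates and either the dependence or the rate differs by arm. This includes a single common rule when treatment works: if poor 9-month change makes leaving more likely, the comparator loses more of its heavier people and the difference shrinks. If the dependence is in one arm only, the bias can go either way. Weights at 6 and 9 months carry information about this, and they are already collected.

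**Working it through.** **1. The plan's own figures.** From Sample size and Table 5: 60 per arm, 51 completers per arm, SD 8.2 kg, pre-post correlation 0.87, difference 2.7 kg, two-sided alpha 0.025, 15% dropout.
- Missing at 18 months: 180 × 0.15 = 27.
- Residual SD: 8.2 × √(1 − 0.87²) = 4.04 kg.
- SE of an arm difference: 4.04 × √(2/51) = 0.80 kg.
- Power: Φ(2.7/0.80 − 2.24) = 0.87, as stated (about 0.86 with a t reference).

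**2. Assumptions, none in the documents.** Correlations (0-6, 0-9, 6-9, 6-18, 9-18 months):
- A: 0.93, 0.90, 0.96, 0.90, 0.93
- B: 0.92, 0.89, 0.94, 0.88, 0.90
- C: 0.93, 0.91, 0.97, 0.92, 0.95

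Arm differences are 1.5 kg at 6 months and 1.8 kg at 9 months. Dropout occurs after month 9, with log-odds rising 0.15, 0.3 or 0.5 per kg of 9-month change. In set A the SD of that change is 8.2 × √(2 × 0.10) = 3.67 kg, so the odds ratios per SD are about 1.7, 3 and 6. The last two are strong.

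**3. Hand check of the bias.** To first order, completers in an arm with dropout rate p and slope g are shifted by −g × p × c. Here c is the covariance of 9- and 18-month weight given baseline. In set A, c = 8.2² × (0.93 − 0.90 × 0.87) = 9.88.
- Dependence in one arm only, g = 0.15, p = 0.15: 0.15 × 0.15 × 9.88 = 0.22 kg.
- Common rule, dropout 13% vs 17%: 0.15 × 0.04 × 9.88 = 0.06 kg.
- Same slope and same rate in both arms: the shifts cancel.

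**4. Simulation.** Two arms of 60, 20,000 trials per main scenario (Monte Carlo SE about 0.006 kg), truth 2.70 kg. Ranges cover sets A-C. The comparison is available-case ANCOVA against the maximum-likelihood longitudinal estimate. Sex is omitted because the plan's SD and correlation are already sex-adjusted.

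| Dropout mechanism | ANCOVA at 0.15 / 0.3 / 0.5 (kg) | Longitudinal (kg) |
|---|---|---|
| Random | 2.70 | 2.70 |
| Same slope, same rate | 2.70 / 2.70 / 2.70 | 2.70 |
| One common rule | 2.65-2.66 / 2.55-2.59 / 2.42-2.50 | 2.70 |
| Comparator only | 2.47-2.52 / 2.28-2.38 / 2.12-2.26 | 2.70 |
| Combined arm only | 2.88-2.93 / 3.03-3.12 / 3.14-3.28 | 2.70 |

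- The largest modest-dependence bias is 2.70 − 2.47 = 0.23 kg, and 0.23/0.80 = 29% of the SE.
- Power: 0.86 vs 0.87-0.89 under random dropout; under a common rule, 0.85 / 0.83 / 0.81-0.82 vs 0.87-0.89.
- Variance of the longitudinal estimate: 5-9% smaller under random dropout, 4-8% smaller under modest dependence that is equal or follows a common rule, about 2% larger at slope 0.5 in those cases.
- With no treatment effect, a common rule leaves false positives at 0.025-0.027. One-arm dependence gives 0.028-0.031 / 0.036-0.046 / 0.048-0.067 against a nominal 0.025.

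**5. Where the longitudinal model helps less or not at all.**
- Dropout driven by unseen regain after month 9 (0.3-0.5 per kg), ANCOVA vs longitudinal: common rule 2.60-2.65 vs 2.56-2.65; comparator only 2.28-2.46 vs 2.09-2.43; combined arm only 2.93-3.12 vs 2.97-3.31. It is no better and sometimes slightly worse.
- Dropouts with no post-baseline clinic weight (set A, comparator only, slope 0.5): the estimate is 2.54 if a third of dropouts are such early leavers and 2.46 if half are, against 2.17 for ANCOVA. The share of bias removed is 0.37/0.53 = 70% and 0.29/0.53 = 55%.

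**6. The plan's baseline-covariate provision** (set A, comparator only, slope 0.3). A covariate correlated 0.3 with 9-month change moves ANCOVA from 2.32 to 2.35, removing 0.03/0.38 = 8% of the bias. One correlated 0.5 moves it to 2.41, removing 0.09/0.38 = 24%.

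**The case against.** **The plan does address attrition, and endpoint ANCOVA is legitimate.** Both are true. The provision, however, is conditional, uses baseline covariates only, and supplies no value or model for a missing weight.

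**Reading the test as available-case is inference from silence.** This is fair as far as it goes. A reader might take the 51 completers per group as proof that only completers will be analyzed. It is a planning figure and proves nothing about the analysis. The supportable statement is that the model as described can use only participants with an 18-month weight, and no alternative is given.

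**The interim weights are not wasted.** This is right for the plan as a whole. The Aim 2 regain regression needs a post-loss weight, and the secondary analyses consider adjusting for initial weight lost. Neither handles a missing Aim 1 outcome.

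**The gain is small and rests on assumptions.** This stands. At modest dependence under a common rule the bias is about 0.05 kg against an SE of 0.80 kg. The larger figures need one-arm dependence or odds ratios of 3 to 6 per SD, and the documents support neither specifically.

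**The model does not help where this trial is most exposed.** This also stands. The trial is about regain in months 10-18, when no clinic weight is taken. For dropout driven by that regain, only a sensitivity analysis that departs from missing at random is informative.

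**Conclusion.** The point holds as a cheap improvement. The Aim 1 test lacks a stated method for missing 18-month weights, and a model that uses the 6- and 9-month clinic weights is available at almost no cost.

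The expected benefit is modest: about 0.05 kg of bias avoided under a common rule at modest dependence, about 0.2 kg (up to 0.23 kg) if the dependence is in one arm, and more if it is stronger. Variance is 4-9% smaller under random or modest dropout. These sizes depend on the assumed correlations, interim differences and dropout slopes.

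A reader might infer that the primary analysis is biased as it stands, or that the trial is underpowered. The documents support neither. Bias requires dropout related to post-baseline weight in a way that differs by arm or comes with unequal dropout rates, and the documents give no dropout pattern. The power of 0.87 reproduces at 51 per arm. Nor would the longitudinal model settle the missing-data problem: it leaves dropout driven by unseen late regain untouched and only partly corrects for people with no post-baseline clinic weight.

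**What to change.** Specify the following before 18-month weights are examined by arm.

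- **Primary model for Aim 1:** a likelihood-based repeated-measures model of clinic weight at 6, 9 and 18 months, with arm × visit, baseline weight × visit and sex × visit, unstructured covariance and Kenward-Roger degrees of freedom. Include all randomized participants with any post-baseline clinic weight. Keep the 18-month arm difference as the primary contrast and keep the Bonferroni adjustment.
- **Sensitivity analyses:** the planned 18-month ANCOVA, and the data-driven stratification on predictors of attrition.
- **Early leavers:** report by arm the number with no post-baseline clinic weight. Weights recorded at group sessions may be used for them in a sensitivity analysis.
- **Delta adjustment:** shift missing 18-month weights in one arm at a time, from 0 to beyond the tipping point, for example 0 to 8 kg. At 15% missing, each 1 kg moves the arm difference by 0.15 kg. With a critical value of 2.28 (about 100 degrees of freedom), a 2.7 kg result tips at (2.7 − 2.28 × 0.79)/0.15 = 6.0 kg to (2.7 − 2.28 × 0.77)/0.15 = 6.3 kg.

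The cost is SAP wording and code, with no new visits or data. The downsides are a little more analysis work, reliance on missing at random (which the delta analysis probes), and about 2% more variance under strong dependence.

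### Single-step Bonferroni on the two primary weight contrasts is valid but needlessly conservative; Holm keeps the same error control and recovers power, and the interval level and the third contrast's status should be stated.

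*Combined protocol and SAP*

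**What the plan says.** Aim 1 in the Objectives contains three pairwise comparisons with different status. Two form the primary hypothesis: "WL+EX+SitLess will have lower 18-mo body weight than either WL+EX or WL+SitLess". The third is labelled separately: "Secondary hypothesis: WL+SitLess will have lower 18-mo body weight than WL+EX".

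The Table 5 caption describes a 0.05 level with a "2-sided test, Bonferroni adjustment for multiple comparisons". Its rows put the primary pair at 0.025 each and the secondary contrast at 0.05. The sample size text says of the secondary contrast that it is "not adjusted for multiple comparisons".

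The Data analyses section specifies ANCOVA of 18-month weight for Aim 1, then gives two sentences: "Differences in least-squares means and associated 95% confidence intervals will be calculated" and "Bonferroni adjustment will be used to account for multiple comparisons". It does not give the number of contrasts adjusted for, say whether the intervals are adjusted, or repeat that the secondary contrast is exempt.

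**The concern.** Two tests each held at 0.025 control the family error, but single-step Bonferroni keeps the second test at 0.025 even after the first has succeeded. Error control does not require that. Holm releases the second test to 0.05 at that stage. It rejects everything Bonferroni rejects and sometimes more. The power lost bears on the trial's main claim, that the combined arm does better than each comparator.

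Two matters of wording go with this. A reader of the analysis section alone cannot tell whether the adjustment covers two or three contrasts, or at what level the intervals will be reported. Both should be settled before the 18-month comparison is made.

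**Working it through.** **Inputs** (Statistical Analyses, Sample size, and Table 5): SD 8.2 kg; pre-post correlation 0.87; 51 completers per arm; differences of 2.7 and 4 kg at two-sided 0.025 (primary) and 2.3 and 2.5 kg at two-sided 0.05 (secondary).

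**Step 1: reproduce Table 5.**
- ANCOVA residual SD = 8.2 × √(1 − 0.87²) = 4.043 kg.
- SE of a pairwise difference = 4.043 × √(2/51) = 0.80 kg.
- Power ≈ Φ(difference/SE − z), with z = 2.241 at 0.025 and 1.960 at 0.05.

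| Difference | Level | Difference/SE | Recomputed power | Table 5 |
|---|---|---|---|---|
| 2.7 kg | 0.025 | 3.372 | 0.871 | 0.87 |
| 4 kg | 0.025 | 4.996 | 0.997 | >0.99 |
| 2.3 kg | 0.05 | 2.873 | 0.819 | 0.81 |
| 2.5 kg | 0.05 | 3.123 | 0.877 | 0.87 |

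The noncentral t with 148 degrees of freedom gives 0.865, 0.997, 0.814 and 0.873. The table reproduces as power for a single contrast.

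**Step 2: family error.** The two primary contrasts share the combined arm, so with equal arms their correlation is 0.5. Simulation of three equal arms (4 million draws) under the global null gives about 0.046 for two tests at 0.025.

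Holm has the same value under the global null, because its first rejection also needs a p-value of 0.025 or less. If only one primary null is true, rejecting it wrongly needs p ≤ 0.05. Holm's family error is therefore at most 5% in every configuration.

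**Step 3: power, Bonferroni against Holm.**

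| True advantage over the two comparators | Quantity | Bonferroni | Holm |
|---|---|---|---|
| 2.7 and 2.7 kg | power per contrast | 0.871 | 0.907 |
| 2.7 and 2.7 kg | win both | 0.789 | 0.861 |
| 4 and 4 kg | win both | 0.994 | 0.998 |
| 4 and 1.7 kg | power for the weaker contrast | 0.45 | 0.565 |

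The last row combines the anticipated 4 kg over WL+EX with Table 5's 2.3 kg for WL+SitLess over WL+EX, which leaves 4 − 2.3 = 1.7 kg over WL+SitLess.

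**Step 4: intervals.** Two unadjusted 95% intervals for the primary contrasts jointly cover with probability about 0.91. Two 97.5% intervals cover jointly at about 0.953 and are wider by 2.241/1.960 = 1.14.

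The 97.5% intervals match Bonferroni exactly but not Holm's second step. Whenever Holm gains over Bonferroni, the 97.5% interval for the second contrast includes zero although Holm rejects. At 2.7 kg each this happens in 0.861 − 0.789 = 0.072 of trials.

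**Step 5: the third contrast.** Adding WL+SitLess against WL+EX at 0.05, with no condition on the primary results, gives an error of about 0.085 over all three tests under the global null. The bound by summing is 0.025 + 0.025 + 0.05 = 0.10. Holm on the primary pair does not change this figure.

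**The case against.** **Bonferroni is valid, so nothing is broken.** This stands. Holm is an efficiency gain and not a correction of error. At the effect the plan anticipates, the gain is negligible. It matters at the smallest difference the plan claims to detect, or when the two advantages are unequal.

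**Holm has a price.** This also stands. No simple fixed-level interval agrees with its second step, so the plan must say which result decides.

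**If the primary hypothesis requires beating both comparators, no adjustment is needed.** Testing each at 0.05 would give 0.865 for both at 2.7 kg, slightly above Holm's 0.861. The wording of the hypothesis does not settle whether both must succeed. The 0.025 split suggests that each contrast may carry a claim alone, and Holm preserves that option.

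**Stronger readings a reader might infer.**
- That the Aim 1 rule contradicts itself and runs at 8.5% error. The documents do not support this. The third contrast is prespecified as secondary, given 0.05 in Table 5 and openly described as unadjusted. The 8.5% pools it with a primary pair that is itself controlled, and the plan nowhere claims control over all three tests.
- That the intervals will contradict the tests. This assumes unadjusted intervals. The Bonferroni sentence directly follows the interval sentence and may cover both.
- That the third contrast must be gated on the primaries. Gating is a trade-off. With advantages of 4 and 1.7 kg, power for the secondary contrast would fall from 0.82 to 0.41 if it had to wait for both primaries to succeed under Holm.

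**Conclusion.** The concern holds as a cheap improvement to a valid rule. Holm would raise the probability of winning both primary contrasts by about 7 points, and power per contrast by about 3.6 points, at a true 2.7 kg against each comparator. The gain is under half a point at 4 kg each. Family error stays at or below 5%.

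These figures rest on Table 5's SD and correlation, 51 completers in each arm, equal residual variance and normal theory. The joint results also depend on the assumed pair of true differences.

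The scope of the adjustment and the interval level need a clarifying sentence. They do not amount to a failure of error control for the primary hypothesis.

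**What to change.** In the Data analyses section, for Aim 1:

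1. Name the two primary contrasts and replace single-step Bonferroni with Holm: the smaller p-value is tested against 0.025 and, if significant, the other against 0.05.
2. State that the Holm test decides significance, and give the level of the reported intervals. If they are unadjusted 95% intervals, note that the two primary intervals jointly cover about 91%. If they are 97.5% intervals, note that one may include zero when Holm rejects at its second step.
3. State that WL+SitLess against WL+EX is tested at 0.05, is not covered by the adjustment and lies outside the controlled primary family, so that error over all three tests would be about 8.5% under the global null.

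Gating the secondary contrast is optional and is not part of this change.

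The cost is SAP wording, with no new participants or data, and the loss of an exact match between test and interval. The change should be made before the 18-month group comparisons are seen.
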